6.2 Dosage, Preparation and Administration of Study Intervention (HPS)^{250, 251}

HPS will be administered through a cannula placed in a large peripheral vein. All participants will already have a peripheral cannula in place for maintenance fluid replacement. Dosage and adjustments in infusion rates will be administered per Standard Operating Procedures.

The HPS saline bag will be connected to a volumetric infusion set. Based on the weight of the subject, and the current sodium concentration, the appropriate amount of HPS will be placed in the chamber and the tubing attached to the secondary port of the intravenous line already in use for delivery of maintenance fluids. Only the amount of fluid to be installed in the current intervention will be delivered to the chamber, to avoid the possibility of overdose.

The HPS loading dose will take place over a 30-minute period, with duration regulated by adjustment of the drop rate. Maintenance fluids will continue during the infusion of the HPS loading dose to minimize the possibility of phlebitis.

After the loading dose is complete, the infusion rate will be reduced to the maintenance infusion rate (see Standard Operating Procedure).

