6.3 Modification of Study Intervention for a Participant (HPS)

Although sodium abnormalities are rare in CM, in the event that a participant has a (Na⁺) level of > 150 mmol/L on admission, the initial bolus will be deferred and the sliding scale dosing detailed in Table 3 will instead be followed.

The subsequent dosing of HPS is planned on a sliding scale, with the goal of maintaining serum sodium levels between 150 and 160 mmol/L. Serum sodium levels will be checked every 3 hours for the first 12 hours of the study, and then every six hours, unless designated otherwise (Table 3).

Table 5. Dosing schedule for hypertonic saline

Serum Sodium	Dose of 3% HPS	Sodium recheck
< 145 mmol/L	5 mL/kg (bolus)*	3 hours
145 – 150 mmol/L	2 mL/kg (bolus)*	3 hours
150 - 160 mmol/L	None	6 hours
>160 mmol/L	Hold infusion until serum sodium is ≤ 155, restart at 0.5 mL/kg/hr	1 hour

*If > 3 boluses are required to maintain serum sodium between 150-160, then increase infusion by 0.25 mL/kg until no further boluses are required.

Further modifications to the HPS dose will be made in the event of the following laboratory abnormalities (electrolyte abnormality grading detailed in Appendix B):

- Grade 4 hypokalemia (see Toxicity Table in Appendix B)
- A pH drop of more than 0.2 within 6 hours
- Chloride > 125 mmol/L
- Serum osmolality > 340 mOsm

In these instances, planned HPS doses will be held, and corrective actions (detailed in Section 9.2.4) will be taken. Electrolytes will be rechecked in 3 hours and the normal dosing schedule will be reinstated if electrolytes are no longer in the Grade 4 toxicity range.

If the pH < 7.25 or falls by 0.2 within 6 hours or if the serum chloride is > 125 mmol/L, the 3% saline infusion will be stopped and converted to a 1:1 ratio of 3% sodium chloride/sodium acetate solution.

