- Sedation: Participants requiring ventilator support will be intubated after induction of anesthesia with ketamine IV ²⁵³ along with diazepam. Atropine will be available in case of bradycardia associated with direct laryngoscopy. While patients remain intubated, they may be pre-treated (at the discretion of the intensivist) with morphine or diazepam or lidocaine prior to noxious stimulation such as endotracheal tube suctioning or placement of gastric tubes, intravenous lines, etc.
- Fluids/Nutrition:
 - At admission, all participants will be placed on maintenance fluids
 - Infusion rates will adhere to the QECH Dept. of Paediatrics protocol: 4mls/hr for the first 10kg, 2ml/hr for next 10kg, 1ml/hr for any weight above 20kg. Adjustments may be performed at the discretion of the intensivist.
 - If a participant remains comatose and is therefore unable to take oral feeds at 36 hours post-randomization, a nasogastric tube will be placed, and a milk-based nutritional supplement will be administered at the same rate as peripheral IV fluids. IV fluids infusion rates will be decreased as NG feed volumes are increased. Nasogastric feeds will be initiated when deemed safe by the PICU physician.
 - 50% Dextrose will be used as a rescue therapy for subjects experiencing hypoglycemia of < 3.0 mmol/L.
- Blood transfusions will be administered as required on clinical grounds.
- Oxygen therapy: Oxygen saturation will be measured continuously in the PICU; it will be measured and recorded on the PRW every two hours by a dedicated study nurse using a portable oxygen monitor with a pediatric finger probe. From the TBI literature adequate

oxygenation is important for treating raised intracranial pressure as injured tissue is highly susceptible to secondary insults including hypoxia²⁵⁴⁻²⁵⁶. Supplemental oxygen will be provided by nasal cannula, endotracheal tube, or mask to maintain peripheral oxygen saturations above 90%.

- Chloral hydrate: Chloral hydrate will be used in children returning for 1-month follow-up visits if sedation is required for the follow-up MRI.
- Omeprazole: Omeprazole may be added at the intensivist's discretion should any participants experience gastrointestinal bleeding. Study Schedule

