9.2.4.2 Hypokalemia

As per the toxicity table attached as Appendix B, a serum potassium measurement of <2.0 mmol/L will be defined as a Grade 4 adverse event. Corrective action will be in the form of adding 40 mmol/L of KCl to the maintenance IV fluids (an increase from the 17mmol/L K⁺ present in ½ Strength Darrow’s). IV fluid infusion rate will remain the same. HPS boluses will continue, and electrolytes will be monitored at 3 hour intervals until K⁺ returns to below Grade 3 disturbances.

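### Two dosing instructions are printed with incomplete units: the maintenance fluid rate has no per-kg term, and the hypertonic saline step-up has no time unit.

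*Combined protocol and SAP*

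**What the plan says.** **Maintenance fluid (section 6.11, Fluids/Nutrition).** All participants receive it from admission. The text states "Infusion rates will adhere to the QECH Dept. of Paediatrics protocol", then prints the rates as "4mls/hr for the first 10kg, 2ml/hr for next 10kg, 1ml/hr for any weight above 20kg", and adds "Adjustments may be performed at the discretion of the intensivist". Two other instructions use this rate:

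- In a child still comatose at 36 hours, "a milk-based nutritional supplement will be administered at the same rate as peripheral IV fluids" (section 6.11).
- For grade 4 hypokalemia, "Corrective action will be in the form of adding 40 mmol/L of KCl to the maintenance IV fluids", with the fluid rate left unchanged (section 9.2.4.2).

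**Hypertonic saline (HPS) step-up (section 6.3, Table 5).** If more than three boluses are needed to hold sodium in range, the footnote says to "increase infusion by 0.25 mL/kg until no further boluses are required". The one infusion rate printed in the table applies after sodium has exceeded 160 mmol/L and the infusion has been held: "restart at 0.5 mL/kg/hr". Section 6.2 also points elsewhere: "Dosage and adjustments in infusion rates will be administered per Standard Operating Procedures".

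Neither the departmental protocol nor the HPS SOP is reproduced in the document.

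**The concern.** A rate built up by weight band would be expected to depend on the kilograms in each band. As printed, it depends only on which band the child reaches. The other weight-based doses written out in section 6.11 (paracetamol, ibuprofen, ceftriaxone) do carry a per-kg term, so the omission stands out within its own section.

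The footnote has a similar gap. A change to a running infusion needs a time unit, and the same table supplies one for its restart rate but not for the step-up.

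The maintenance instruction reaches every child and feeds into two further instructions. The footnote concerns the experimental product. Section 6.5 makes irregular HPS administration a reportable deviation, and section 15.6 defines deviations as noncompliance with the protocol or the manual of procedures. An instruction with an incomplete unit cannot serve as the standard against which adherence is judged.

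**Working it through.** The plan states no total rate, so there is no figure of its own to reproduce. The check applies the printed rule under two readings.

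**Inputs.** Band figures 4, 2 and 1 (section 6.11); KCl at 40 mmol/L (section 9.2.4.2); restart rate 0.5 mL/kg/hr and step-up 0.25 mL/kg (section 6.3, Table 5). The documents give an age range of 6 months to 12 years but no weights, so every weight below is an assumption.

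**Maintenance fluid.**

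- Literal reading: add the rate of each band that the child's weight enters. Summing the bands is itself an assumption.
- Per-kg reading: multiply each band's rate by the kilograms in that band, then add.

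| Assumed weight (kg) | Literal (mL/hr) | Per-kg reading (mL/hr) | Ratio |
|---|---|---|---|
| 7 | 4 | 4×7 = 28 | 7.0 |
| 10 | 4 | 4×10 = 40 | 10.0 |
| 15 | 4+2 = 6 | 40+2×5 = 50 | 8.3 |
| 20 | 4+2 = 6 | 40+2×10 = 60 | 10.0 |
| 30 | 4+2+1 = 7 | 60+1×10 = 70 | 10.0 |
| 35 | 4+2+1 = 7 | 60+1×15 = 75 | 10.7 |
| 40 | 4+2+1 = 7 | 60+1×20 = 80 | 11.4 |

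On the literal reading, children of 15 and 20 kg receive the same rate, as does every child above 20 kg. The daily amount per kilogram falls with weight: 4×24/10 = 9.6 mL/kg at 10 kg, 6×24/20 = 7.2 at 20 kg, and 7×24/30 = 5.6 at 30 kg.

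**Dependent instructions, at an assumed 20 kg.**

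- Feed at the same rate: 6 or 60 mL/hr.
- Added KCl: 40 mmol/L × 0.006 L/hr = 0.24 mmol/hr, or 40 × 0.060 = 2.4 mmol/hr.

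**HPS step-up, at an assumed 20 kg.** 0.25 × 20 = 5 mL. Without a time unit this is a volume, not a change of rate. As an hourly step it would be 5 mL/hr. The restart rate, in complete units, is 0.5 × 20 = 10 mL/hr.

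**Search for the missing units.** No other section of the document supplies the per-kg term or the time unit.

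**The case against.** The strongest reply is that neither line stands alone. The maintenance rate is attributed to a departmental protocol and may be adjusted by the intensivist. HPS dosing and rate adjustments are assigned to the SOP. Trained staff may already be using complete rates. This stands as a limit on what can be concluded about bedside practice. It does not supply the missing units: section 6.11 presents its digits as the departmental rates, and discretion to adjust presupposes a clear starting rate.

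It can also be said that an hourly step is the natural reading of the footnote, since it modifies a running infusion in a table whose one infusion rate is hourly. That is fair, and it makes the second omission the milder one. The unit is still absent.

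A reader might be tempted further than the documents allow:

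- **That the printed maintenance rate is the wrong value.** At 20 kg the HPS restart rate (10 mL/hr) exceeds the literal maintenance rate (6 mL/hr), which looks odd. But it is only a restart rate, and nothing requires HPS to run slower than maintenance fluid. Section 6.2 keeps maintenance fluid running during the loading dose without stating a rate. There is no contradiction here, only an incomplete unit.
- **That the footnote is the sole rule for raising the HPS infusion.** Section 6.2 places rate adjustments in the SOP. The footnote is at most the only such rule printed here.
- **That a misreading would leave children below target and trigger the section 9.5 halting rule of five failures to reach 150-160 mmol/L.** Table 5 continues to call for boluses with 3-hour rechecks whenever sodium is below range, however the footnote is read. That consequence is speculative.
- **That the discrepancy is uniformly tenfold.** The ratio depends on weight, and the weights are assumed.

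**Conclusion.** The point holds as an internal consistency and units error in two dosing instructions. No calculation in the plan fails. The maintenance rule lacks a per-kg term in all three bands; the literal and per-kg readings differ about 7- to 11-fold over assumed weights of 7 to 40 kg, and the feed and potassium instructions inherit that gap. The HPS step-up lacks the time unit that the restart rate in the same table carries. Which values were intended cannot be settled from the documents, because the two governing sources are not reproduced.

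This is worth correcting because it concerns the care of comatose children and the delivery of an experimental product. The maintenance wording is common to all arms. Nothing here alters sample size, power or type I error.

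**What to change.** Reconcile the section 6.11 maintenance rates with the departmental protocol cited there, and the Table 5 footnote with the rest of Table 5 and with the HPS SOP. Restate both with complete units. Then check that the nasogastric feed instruction (section 6.11) and the KCl correction (section 9.2.4.2) give the intended amounts once the maintenance rate is restated. The clinical team confirms all values.

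The cost is two wording corrections and a check of two dependent instructions, with the ethics approval that section 14.2 requires for any amendment. Design, enrollment and analysis do not change.

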7 STUDY SCHEDULE

7.1 Screening

Participants admitted to the PRW who meet the following initial inclusion criteria will be approached for consent to further screening.

- Peripheral *P. falciparum* parasitemia of any density
- Blantyre Coma Score ≤ 2
- No evidence of meningitis on lumbar puncture
- Does not regain consciousness after correction of hypoglycemia (if hypoglycemia was present)
- Age between 6 months and 12 years
- Oxygen saturation $\geq 85\%$ on room air
- Capillary refill ≤ 3 seconds and absence of abnormal skin tenting

The decision to approach the parent/guardian for screening will only be made after the participant has been stabilized clinically and anti-malarial therapy commenced. In the context of obtaining informed consent, the wide spectrum of CM disease presentation will be explained and our desire to perform two more exams (a retinal exam and an MRI) to further characterize the child's illness will be presented. The fact that neither of these exams are treatment, but that they might lead to further treatment, will be explained.

If the parent/guardian consents to the screening exams, mydriatic eye drops will be added to the participant's eyes and a direct and indirect ophthalmologic exam will be performed. The participant will be taken to MRI.

7.2 Enrollment/Baseline

If initial inclusion criteria for randomization are met (severely increased brain volume is confirmed on MRI), the parent/guardian will be approached for consent to participate in the clinical trial.

Initial evaluations to be completed at the time of enrollment are detailed in the Schedule of Events attached as Appendix A.

7.3 Follow-up

The first follow up visit will be scheduled for 1 month after randomization. The participant will undergo detailed physical, neurological, and developmental examinations performed by a pediatric neurologist (or their designee), a repeat MRI, NIRS measurements of cerebral oxygenation and muscle reperfusion, and a repeat ONSD determination.

Subsequent visits will be scheduled for 6- and 12-months post-randomization, at which time the patient will undergo detailed physical and neurological, and developmental examinations performed by a pediatric neurologist or their designee. The 12-month post-randomization visit will be the final visit.

All follow-up visits will be performed \pm 14 days from the scheduled post-randomization visit date.

7.4 Final Study Visit

As described in Section 7.3, the final study visit will occur at the 12-month (\pm 14 days) post-randomization follow-up visit. Evaluations to be completed at follow up are detailed in Appendix A – Schedule of Events.

7.4.1 Death

If a death occurs in any of the study arms, transportation will be provided for the deceased and the family.

7.5 Early Termination Visit

If a participant/parent/guardian elects to terminate the study, or study participation is terminated early due to any of the events listed in Section 9.2.3, the parent/guardian will be asked if they are willing to have another MRI performed. They will also be asked if they would be willing to return to the PRW at 1 month (\pm 14 days) post-randomization, as this is standard-of-care for all participants on the PRW.

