3.2.2 Secondary Outcome Measures

1. Neurological sequelae in survivors, assessed at 1, 6, and 12 months after randomization via the Malawi Developmental Assessment Tool (MDAT) for participants up to the age of 59 months old, and the Kaufman Assessment Battery for Children, Version II (KABC II) for participants over the age of 59 months. All survivors will also be assessed using the Glasgow Outcome Scale (GOS)²⁴⁷. The GOS is a global scale for functional outcome that rates patient status into one of five

categories: dead, vegetative state, severe disability, moderate disability or good recovery.

2. Surrogate measures of increased brain volume: At the time of admission (only): opening CSF pressure, archived samples of blood, urine and CSF. Daily while comatose: ophthalmoscopy for papilledema (present/absent), optic nerve sheath diameter in mm, NIRS measurements of cerebral oxygenation and muscle reperfusion, standardized neurologic observations.
3. Standard TCD phenotypes: microvascular obstruction, hyperemia, vasospasm, low flow, isolated posterior hyperemia). Potential mechanisms: increased brain volume per MRI/ischemic changes, hypercapnia/acidosis/seizures, localized ischemia on MRI, compromised hemodynamics/diminished compensatory reserve/increased brain volume per MRI

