5.3.3 Reasons for Withdrawal

A study subject will be withdrawn from the study if:

- A screening error is discovered that resulted in incorrect enrollment (subject did not meet inclusion or exclusion criteria)
- CSF from admission lumbar puncture results in growth of pathogenic bacteria
- Parental consent is withdrawn at any stage for any of the procedures or treatment
- It is discovered that the participant has an intercurrent illness that, when combined with the study interventions, might compromise the recovery of the patient
- Safety reasons as judged by the investigator, ISM, or DSMB

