5.3.4 Handling of Withdrawals

Participants withdrawn from the study will remain on the PICU/PRW and will continue to benefit from the increased level of clinical care provided. If the participant is withdrawn due to an adverse event (AE; see section 9 below for more details), laboratory monitoring will continue until the event resolves. Participants will continue to have brain volumes evaluated by multiple modalities as long as this is deemed non-injurious. Participants will still be scheduled for a 28-day post randomization follow up visit and measures of neurologic sequelae and brain volume will be collected. If the participant is voluntarily withdrawn from the study by the parent/guardian, all efforts will be made to encourage the participant to return for 28-day post-randomization follow up.

Attempts will be made to recruit additional participants to replace any participants that withdraw prior to reaching the 12-month post-randomization visit. At the conclusion of the study separate analyses will be run on per-protocol and intention-to-treat populations.

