Three other study radiologists will review all screening and study scans and will arrive at a consensus ‘brain volume score’ for each MRI scan on a regular basis and will complete the task within 1-month of the end of the enrollment period each year. If there is a discrepancy regarding the initial brain volume score and the consensus score in enrolled subjects any subjects incorrectly enrolled will be excluded from the ‘per protocol’ analyses but will remain in the ‘intention to treat’ analyses. If there is a discrepancy in the serial MRIs that affects the decision to withdraw the experimental treatment (VENT or HPS), the discrepancy will be noted; any subjects incorrectly withdrawn will be excluded from the ‘per protocol’ analyses, but will remain in the ‘intention to treat’ analyses.

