9.2.3 Serious Adverse Events

An adverse event or suspected adverse reaction is considered "serious" if, in the view of either the investigator or sponsor, it results in any of the following outcomes:

- Death,
- A life-threatening adverse event,
- Hospitalization or prolongation of existing hospitalization,
- A persistent or significant incapacity or substantial disruption of the ability to conduct normal life functions, or
- A congenital anomaly/birth defect.

Important medical events that may not result in death, be life-threatening, or require hospitalizations may be considered serious when, based upon appropriate medical judgment they may jeopardize the participant and may require medical or surgical intervention to prevent one of the outcomes listed in this definition. Only events that are not attributable to the malarial illness, that are outlined in section 2.4.1.2, or that were unanticipated, but that are considered to be possibly related to the study intervention will be graded and reported as Adverse Events to the sponsor, IRBs, and independent safety monitors.

- Life-threatening adverse event: An adverse event is considered “life-threatening” if, in the view of either the investigator or sponsor, its occurrence places the participant or subject at immediate risk of death. It does not include an adverse event, had it occurred in a more severe form, might have caused death.

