9.3 Reporting Procedures

9.3.1 Serious Adverse Events

The reporting period for SAEs will be between the time of randomization and the twelve month (± 2 weeks) post-randomization follow up visit.

SAE reporting will be carried out as follows

The study clinician will complete a Serious Adverse Event Form (Appendix D) and SAEs thought to be related to study related procedures will be reported within 24 hours of their recognition, to the independent safety monitor, the IRBs at Michigan State University and the University of Malawi College of Medicine, and the sponsor, unless advised otherwise by the DSMB.

Any AE that meets a protocol-defined serious criterion will be submitted on an SAE form to the DMID Pharmacovigilance Group, at the following address:

DMID Pharmacovigilance Group
Clinical Research Operations and Management Support (CROMS)
[name]
[name]
SAE Hot Line: [name] (US) or [name] (outside US)
SAE FAX [contact] (US) or [name] (outside US)
SAE Email Address: [contact]

Other supporting documentation of the event may be requested by the DMID Pharmacovigilance Group and will be provided as soon as possible.

The DMID medical monitor and clinical protocol manager will be notified of the SAE by the DMID Pharmacovigilance Group. The DMID medical monitor will review and assess the SAE for regulatory reporting and potential impact on study subject safety and protocol conduct.

At any time after completion of the study, if the investigator becomes aware of an SAE that is suspected to be related to study product, the investigator will report the event to the DMID Pharmacovigilance Group, the independent safety monitor, and the IRBs of the University of Malawi and Michigan State University.

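### Sections 5.3.3, 5.3.4 and 7.5 do not separate stopping the intervention from leaving the study, and they conflict with the 12-month follow-up planned elsewhere

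*Combined protocol and SAP*

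**What the plan says.** **Rules for children who withdraw or are terminated**

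- Section 5.3.3 lists grounds for withdrawal from the study: a screening error, a positive CSF culture, an intercurrent illness that could compromise recovery in combination with the study interventions, a safety judgement, and "Parental consent is withdrawn at any stage for any of the procedures or treatment".
- Section 5.3.4 says of these children: "Participants will still be scheduled for a 28-day post randomization follow up visit". Neurological sequelae are measured at that visit. It names no 6- or 12-month visit. It adds: "Attempts will be made to recruit additional participants to replace any participants that withdraw prior to reaching the 12-month post-randomization visit".
- Section 7.5 describes what to offer if a guardian ends participation or if "study participation is terminated early due to any of the events listed in Section 9.2.3". The offer is a further MRI and a return at 1 month, both only if the guardian is willing. The list in 9.2.3 is the set of SAE criteria. One of them is "A persistent or significant incapacity or substantial disruption of the ability to conduct normal life functions".

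**Text that points to 12 months for everyone**

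- Section 3.2.2: "Neurological sequelae in survivors, assessed at 1, 6, and 12 months after randomization".
- Section 4 keeps survivors in the study until the 12-month visit.
- Section 9.1 makes long-term neurological sequelae a safety assessment covering all participants.
- Section 9.3.1: "The reporting period for SAEs will be between the time of randomization and the twelve month" visit.
- Section 9.4, on follow-up after adverse events, has all participants asked back at 1, 3, 6 and 12 months.
- Section 8.3.2 keeps children later found to be incorrectly enrolled in the intention-to-treat analysis. The radiologists who make the consensus reads "will complete the task within 1-month of the end of the enrollment period each year".

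**The concern.** Nothing in 5.3.3, 5.3.4 or 7.5 allows a child to stop the intervention and still be a trial participant. If those sections are followed as written, follow-up ends at about 1 month for children whose reason for leaving may be tied to treatment and to prognosis.

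The link to arm is visible in the text. The intercurrent-illness ground in 5.3.3 depends on combination with the study interventions, so it can arise in VENT and HPS but hardly in usual care. The reporting limits in 9.2.3 also turn largely on relation to the intervention.

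What is at stake is the later neurological outcome. Section 2.3 warns that ventilatory support may produce survivors with severe sequelae, and Section 4 counts severely impaired survival among the reasons for a DSMB. The 6- and 12-month assessments are the trial's longer-term evidence on that harm. Visits that are never scheduled cannot be recovered at analysis.

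**Working it through.** The plan states no dropout allowance, SAE rate or termination rate, so there is no figure to reproduce. The check is a comparison of passages, followed by an illustration on assumed inputs.

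**1. Which instruction governs?** Sections 4, 9.1 and 9.4 are general. Sections 5.3.4 and 7.5 are the specific instructions for withdrawn or terminated children, so staff could reasonably follow those. Section 9.4 is also a weak anchor, because it includes a 3-month visit that 7.3 does not schedule. The documents do not say which text prevails.

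**2. Does it matter whether 7.5 meant to cite 9.2.3?** If 9.2.3 is intended, SAE criteria are a possible ground for ending participation. If the reference is a slip for 5.3.3, the same children fall under the 28-day rule in 5.3.4. Either way, no 6- or 12-month visit is named for them.

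**3. Screening errors.** Section 5.3.3 withdraws a child enrolled through a screening error, while 8.3.2 keeps incorrectly enrolled children in intention-to-treat. Section 2.3 gives the first enrollment season as January to June. On that calendar, consensus reads finish by the end of July. A child randomised in early January is then about 7 months out, so every 12-month visit is still ahead. So are the 6-month visits of children randomised from about February on (end of July minus 6 months = end of January). A withdrawal at that point would lose visits that intention-to-treat needs.

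**4. Replacement.** The primary outcome is fixed by day 7 (3.2.1). Replacing a child who leaves between day 7 and month 12 adds a child to the 7-day sample and does not restore the lost 12-month assessment.

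**5. Illustration of size.**

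Survivors per arm:

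- The projected intervention arm is 32 (Section 4, projected enrollment).
- Mortality is taken from 14% (the target in 11.6) to 36% (the usual-care estimate in Section 4 and 11.5).
- 32 × (1 − 0.14) = 27.5 and 32 × (1 − 0.36) = 20.5, so about 20 to 28 survivors.

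Let f be the share of survivors terminated, q_t their sequelae risk, and q_r the risk in those retained. All three are assumed.

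- True rate = f·q_t + (1 − f)·q_r.
- Observed rate = q_r.
- Understatement = f·(q_t − q_r).

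With q_r = 20%:

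| f | q_t | Understatement |
|---|---|---|
| 2% | 25% | 0.02 × 0.05 = 0.1 points |
| 5% | 50% | 0.05 × 0.30 = 1.5 points |
| 10% | 50% | 0.10 × 0.30 = 3 points |
| 20% | 75% | 0.20 × 0.55 = 11 points |

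With about 25 survivors, f of 2-20% is 25 × 0.02 = 0.5 to 25 × 0.20 = 5 children per arm.

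**The case against.** The strongest reply is that the protocol already intends 12-month follow-up for everyone. Section 9.4 says so in the very section on follow-up after adverse events, and Sections 4, 9.1 and 9.3.1 agree. This stands: loss is a risk created by contradictory text, not a certainty.

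Several stronger readings are tempting, and the documents do not support them.

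- *That 7.5 ends participation after an SAE.* The sentence is conditional. It says what to offer if participation ends, and 5.3.3 lists no SAE as such, only a safety judgement. The reference to 9.2.3 may be a slip, since other cross-references are off (5.3.5 sends the interim analysis to 11.3, but it is in 11.6).
- *That the most impaired children will be the ones lost.* The SAE list includes lasting incapacity, but 9.2.3 limits reportable events largely to those not attributed to malaria or possibly related to the intervention. Ordinary sequelae of cerebral malaria are not shown to trigger termination.
- *That 11.7.1 considers only missingness explained by observed data.* It also proposes to investigate inverse-probability weighting for other patterns, and the 28-day neurological measure would be an observed predictor of later status. It does, however, call missing responses quite unlikely and specifies no weighting model. With 20 to 28 survivors per arm, this is not a dependable remedy.
- *That the 2018 re-reads in Section 2.3 give a rate of late ineligibility.* The re-reads of real-time scores of 5 or 6 concern children below the score of 7 that made a child eligible that season. Nor is a later consensus disagreement plainly a screening error, because eligibility rests on two real-time reads.
- *That replacement biases the primary comparison.* Section 5.3.4 plans an intention-to-treat analysis, and no bias follows if the replaced child stays in it. What stands is that replacement does not repair the later outcome.

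**Conclusion.** The point holds as an internal contradiction with a practical consequence. The specific withdrawal rules stop planned follow-up at about 1 month. The general text expects 12 months, and 8.3.2 expects incorrectly enrolled children to stay in intention-to-treat. If the specific rules are followed, 6- and 12-month sequelae data are lost for reasons that may depend on arm and prognosis.

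The exposure is limited to a secondary and safety outcome at those two visits.

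The illustrated understatement spans two orders of magnitude and rests wholly on assumed termination shares and sequelae risks. It shows that the loss could be negligible or material, and no single value in the range should be quoted as an expected bias. Severity is moderate. The case for acting is that the correction is cheap and the data cannot be recovered afterwards.

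**What to change.** Amend 5.3.3, 5.3.4 and 7.5 so that they agree with Sections 4, 8.3.2, 9.1, 9.3.1 and 9.4:

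1. Define two separate states: the child stops the study intervention, or the guardian withdraws consent for follow-up.
2. Correct or remove the 9.2.3 reference in 7.5 as a ground for ending participation.
3. State that refusal of one procedure stops only that procedure.
4. Keep every randomised child whose guardian still agrees on the 1-, 6- and 12-month visits and in intention-to-treat under the assigned arm. This includes children found later to have been incorrectly enrolled.
5. Limit replacement to withdrawals before the 7-day outcome is known, and keep replaced children in intention-to-treat under their assigned arm. Section 5.3.1 has its own, narrower wording on additional enrollment, which should be made to agree.

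When the intervention itself is stopped stays with the investigators; none of this alters that decision.

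The cost is amendment wording. The visits are already scheduled and no procedure is added. The downside is slightly more tracing effort for a few children.
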